## Statistical analysis plan JUMPER-study

Participants will be analyzed by intention-to-treat. To test for the effect on the between-group difference in primary outcome (VISA-P score), we will use the Generalized Estimating Equation (GEE) model. Adjustments will be made for the following baseline variables: age, sex, BMI, duration of symptoms and activity level (Cincinnati Sports Activity Scale). The same approach will be used for the following secondary outcomes: VAS score on palpation of the proximal patellar tendon, VAS score in the patellar tendon during single leg decline squat before and after isometric exercises, VAS score during the latest sport activity, VAS score during activities of daily living, muscle force and flexibility of upper and lower leg muscles, vertical jump height and two dimensional video-based analysis of the drop vertical jump test.

Compliance to the exercise therapy and the amount of experienced pain (VAS 0-10) will also be analyzed in a secondary analysis to test for the effect of compliance on the primary outcome using the GEE-model.

This GEE-model will also be used to determine the association between the following variables and the course of symptoms resulting from patellar tendinopathy: the level of passive coping (measured with the Pain Coping Inventory) and presence of a neuropathic pain component (measured with the painDETECT questionnaire).

Fisher's exact test will be performed for the following categorized secondary outcomes: return to desired sport and subjective patient satisfaction, which we will dichotomize, for the following categories (A) return to desired sport at pre-injury level, (B) return to desired sport, but not at pre-injury level, (C) return to sport, but not to desired sport, (D) no return to sport and (A) excellent, (B) good, (C) moderate, (D) poor, respectively. For example, return to desired sport at pre-injury level (1) and other categories as (0) and excellent/good as satisfied (1) and moderate/poor as dissatisfied (0), for return to sport and subjective patient satisfaction respectively.

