Missing data will not be imputed to avoid the introduction of biased estimates of treatment effect. We chose this approach because it is likely that missing data will not occur at random. This assumption is based on the facts that patients are not blinded to the allocated therapy and one exercise program is expected to cause significantly more pain than the other exercise program. Therefore, only a sensitivity analysis will be performed if missing data is more than 5%, blinded for the allocated exercise therapy.

We intend to publish results of this study in multiple papers, given the large amount of data derived from this randomized controlled trial.

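### The no-imputation rule is not limited to outcomes, so read literally it removes participants who lack a single baseline covariate from the adjusted GEE models

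*SAP*

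**What the plan says.** The SAP has one section, *Statistical analysis plan JUMPER-study*. Its opening paragraph sets the analysis set: "Participants will be analyzed by intention-to-treat". For VISA-P it specifies "we will use the Generalized Estimating Equation (GEE) model", and it continues: "Adjustments will be made for the following baseline variables: age, sex, BMI, duration of symptoms and activity level (Cincinnati Sports Activity Scale". The adjusted model extends beyond the primary outcome: "The same approach will be used for the following secondary outcomes", followed by a list of pain scores, muscle force and flexibility, jump height and video analysis.

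The missing-data paragraph then gives a general rule: "Missing data will not be imputed to avoid the introduction of biased estimates of treatment effect". The reason offered is that missingness is probably not random, because "patients are not blinded to the allocated therapy and one exercise program is expected to cause significantly more pain than the other exercise program". The only other provision is a sensitivity analysis, blinded to allocation, if more than 5% of data are missing. The paragraph does not separate outcomes from covariates, and it names no other handling for a missing covariate, such as a missing-indicator or a reduced covariate set.

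**The concern.** The five covariates are measured once and are constant over a participant's visits. If one is missing, no row of that participant can enter the adjusted GEE, however complete the outcome data are. A missing outcome at one visit costs only that visit. An unqualified ban on imputation therefore falls harder on a blank baseline field than on a missed follow-up.

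The reasons for the rule do not support that result. Knowledge of the allocated programme, and pain from doing it, can influence data only after allocation. A baseline value cannot be missing because of either, so filling it without using arm or outcome does not bring in the bias that the SAP wants to avoid.

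At stake are the precision of the primary and listed secondary comparisons, and how close the analysed set stays to the randomised set. A different model for missing outcomes, such as a mixed model, would not solve this, because it too needs complete covariates.

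**Working it through.** The SAP gives no sample size, power or missing rate, so there is no figure of its own to reproduce. Two checks apply.

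**1. Does one missing covariate remove the whole participant?** A GEE with exchangeable correlation was fitted to simulated data. The size is an assumption: 80 participants with 3 visits each, so 240 rows, and every outcome observed.

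- Three participants were each given one missing baseline covariate. The adjusted model used 77 of 80 participants and 231 of 240 rows. The loss is 3 × 3 = 9 rows, all of them with observed outcomes.
- For contrast, a model without covariates and with one outcome missing at one visit used 239 of 240 rows and all 80 participants.

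**2. How many participants could be lost?** Let m be the assumed missing rate per covariate and k the number of covariates that can be missing. Age and sex are rarely missing, so k = 3 (BMI, symptom duration, activity level).

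- Gaps all in the same people: loss = m.
- Gaps independent: loss = 1 − (1 − m)^k.
- Gaps never in the same person: loss = k × m.

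If information is proportional to the number of participants, the standard error grows by the factor 1/√(1 − loss).

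| Assumed m | Full overlap | Independent | No overlap |
|---|---|---|---|
| 0% | 0% | 0% | 0% |
| 1% | 1% | 1 − 0.99³ = 3.0% | 3% |
| 2% | 2% | 1 − 0.98³ = 5.9% | 6% |

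For the independent case the standard error rises by 1/√0.970 − 1 = 1.5% at m = 1%, and by 1/√0.941 − 1 = 3.1% at m = 2%. Under full overlap the rises are 1/√0.99 − 1 = 0.5% and 1/√0.98 − 1 = 1.0%.

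If covariates are filled in, the loss due to covariates is 0% at any m.

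**The case against.** The strongest reply is that the missing-data paragraph never mentions covariates. Its reasons are about what happens after allocation, so the natural reading is that the authors had outcomes in mind. On that view the SAP is merely silent on covariates, and the harm is hypothetical because nothing suggests that baseline data will be incomplete. Much of this stands. The rule is too broadly worded, and it should not be read as a decision to exclude anyone. But an analyst has to follow the text, and the text bars imputation without exception and offers no alternative for a covariate.

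A reader might infer more than the SAP supports, in four ways:

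- **A large loss.** With 5% missing in each of all five covariates, independence gives 1 − 0.95⁵ = 22.6% lost, and an assumed 80% power would fall to about 69%. This needs gaps of that size even in age and sex, no clustering of gaps within people, and a starting power that the SAP does not state.
- **A biased comparison, or a flat contradiction of intention-to-treat.** Missingness in a value recorded before allocation should not depend on arm, and dropping the record moves nobody between arms. The cost is mainly precision and some departure from the randomised set.
- **Every GEE is affected.** Adjustment is stated for VISA-P and the listed secondary outcomes. For the analyses of compliance, passive coping and neuropathic pain, the covariates are not stated.
- **The 5% sensitivity analysis as a safeguard.** Its method is not given, the SAP does not say whether covariates count towards the 5%, and it leaves the primary model unchanged.

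**Conclusion.** The point holds as a minor one. Read literally, the rule drops participants with observed outcomes from the adjusted GEE for VISA-P and the listed secondary outcomes when one baseline covariate is missing, for reasons that do not apply to baseline data. On assumed rates of 1% to 2% in three covariates, the loss is about 1% to 2% of participants with full overlap and 3.0% to 5.9% under independence. It is nil if baseline data are complete. These rates are assumptions, and the SAP neither supports nor rules them out. The mechanism, by contrast, follows from the model and the wording alone.

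**What to change.** Add to the missing-data paragraph that the no-imputation rule does not apply to baseline covariates. Word this so that it does not endorse the rule for outcomes, where missingness that the SAP itself expects to be non-random is a separate and more serious question.

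Then state the handling: any missing covariate is filled by single imputation, with the overall mean or a regression on the other baseline variables, using neither arm nor outcome. A covariate entered as categories needs the regression form. Every randomised participant with outcome data then stays in the adjusted model. Report the complete-covariate result alongside as a check.

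The cost is one or two sentences and trivial programming. If no covariate is missing, the results do not change.
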